## 5.2.2 Contraindications for 2.5 mg Rivaroxaban:

- hypersensitivity to the active substance or to any of the excipients
- active clinically significant bleeding
- lesion or condition, if considered to be a significant risk for major bleeding, this may include
  - current or recent gastrointestinal ulceration,
  - presence of malignant neoplasm at high risk of bleeding,
  - recent brain or spinal injury, recent brain, spinal or ophthalmic surgery,
  - recent intracranial haemorrhage,
  - known or suspected oesophageal varices, arteriovenous malformations, vascular aneurysms or major intraspinal or intracerebral vascular abnormalities.
- concomitant treatment with any other anticoagulants e.g. unfractionated heparin (UFH), low molecular weight heparins (enoxaparin, dalteparin, etc.), heparin derivatives (fondaparinux, etc.), oral anticoagulants (warfarin, dabigatran etexilate, apixaban, etc.) except under the circumstances of switching therapy to or from rivaroxaban or when UFH is given at doses necessary to maintain an open central venous or arterial catheter
- concomitant treatment of ACS with antiplatelet therapy in patients with a prior stroke or a transient ischaemic attack (TIA)
- hepatic disease associated with coagulopathy and clinically relevant bleeding risk including cirrhotic patients with Child Pugh B and C
- chronic renal failure with eGFR < 15 ml/min (MDRD formula)

- as with other antithrombotics, rivaroxaban is not recommended in patients with an increased bleeding risk such as:
  - congenital or acquired bleeding disorders
  - uncontrolled severe arterial hypertension
  - active ulcerative gastrointestinal disease
  - vascular retinopathy
  - bronchiectasis or history of pulmonary bleeding
- pregnancy and breast feeding

## 5.3 Description of the IMP – Aspirin (ASS 100) (control group)

The IMP ASS 100 TAH of the control group will be preferably used from ratiopharm GmbH. If it becomes necessary (from indefinable reasons), instead of ratiopharm, Aspirin® Bayer or ASS 100 mg of HEXAL can be used as a control IMP in the same dosage. Both medications have an identical authorization profile.

Trade name:	ASS-ratiopharm ® 100 mg TAH
INN (International Nonproprietary Name)	acetylsalicylic acid
Galenical form / formulation	film coated tablet (white, round table with one-sided cross)
Strength	100 mg
Further contents	cellulose
Type of packaging and content	cartons of 50 tablets
Manufacturer	ratiopharm GmbH
Marketing authorization holder	ratiopharm GmbH

#### TABLE 8: IDENTIFICATION OF THE IMP ASPIRIN

For dosage 100 mg of aspirin it is necessary to administer one tablet once a day at intervals of 24 h.

#### 5.3.1 Indication:

Aspirin 100 mg is indicated for

- Angina pectoris
- acute coronary syndrome
- acute myocardial infarction
- prophylaxis of reinfarction after vascular surgery or PCI
- prophylaxis of stroke or TIA after the occurrence of prior events

### 5.3.2 Contraindications of ASS 100 mg:

Aspirin 100 mg is contraindicated for

- hypersensitivity to the active substance or to any of the excipients
- prior asthmatic episodes in response to salicylates
- gastrointestinal bleeding in medical history, caused by nonsteroidal antiinflammatory drugs
- current or recent gastrointestinal ulceration, with documented bleeding
- increased predisposition to bleeding
- liver or kidney failure
- severe congestive heart failure
- combination with methotrexate  $\geq$  15 mg per week
- during the last trimester of pregnancy

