# 4.7 Justification of selection criteria

The selection criteria are chosen to ensure that subjects with specific risks for administration of the study medication and / or subjects with conditions which may have an impact on the aims of the study are excluded.

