# 4.8 Withdrawal of trial subjects after trial start

#### 4.8.1 Withdrawal

Subjects will be withdrawn from the study for the following reasons:

- at their own request; at any time during the study and without giving reasons, a subject may decline to participate further. The subject will not suffer any disadvantage as a result
- if, in the investigator's opinion, continuation of study would bear a potential health risk for the patient
- at the specific request of the sponsor
- in case of violation of in- / exclusion criteria; if the subject develops conditions which would have prevented his/her entry into the study according to the in- / exclusion criteria, she / he must be withdrawn immediately if safety is concerned; in other cases, the investigator will decide whether there is a conflict with the study objectives
- non-compliance with the study conditions or instructions from the investigator's team
- in case of suspected or verified pregnancy

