# 5.8 Assignment of trial subjects to treatment groups

All eligible patients will be randomized at baseline visit V1 (after necessary laboratory parameters are available) using a central block randomization process based at the sponsor's site. The study site requesting randomization of a patient will send a form containing site ID and screening number to the sponsor (Dept. of Medical Consulting; [contact]**, in the time frame Monday to Friday 8.00 am to 4.00 pm, not on legal holidays). In return, the site will receive a randomization form containing the randomization number and allocation to treatment arm by fax or email within 30 min.

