## 7.3 Data quality

## 7.3.1 Monitoring

The trial site will be monitored to ensure the quality of the data collected. The objectives of the monitoring procedures are to ensure that the trial subject's safety and rights as a study participant are respected, that accurate, valid and complete data are collected, and that the trial is conducted in accordance with the trial protocol, the principles of GCP and local legislation.

All investigators agree that the monitor will regularly visit each trial site and assure that the monitor will receive appropriate support in his activities at the trial site, as agreed in separate contracts with each site. The declaration of informed consent includes a statement to the effect that the monitor has the right – while observing the provisions of data protection legislation – to compare the eCRFs with the trial subject's medical records (physicians notes, laboratory printouts etc.). The investigator will ensure access for the monitor to all necessary documentation for trial-related monitoring. The purposes of the monitor visits are as follows:

- check the informed consent
- check inclusion and exclusion criteria
- monitor trial subject safety (occurrence and documentation/reporting of AEs and SAEs)
- check the completeness and accuracy of entries on the eCRFs
- validate the entries on the eCRFs against those in the source documents (source data verification)
- perform drug accountability checks
- evaluate the progress of the trial
- evaluate compliance with the trial protocol
- assess whether the trial is being performed according to GCP at the trial site
- discuss with the investigator aspects of trial conduct and any deficiencies found.

Monitoring at each trial site will be done for 100 % for the ISF, the patient's informed consent, all in- and exclusion criteria, safety parameters and the drug accountability.

Source data, pre-exisiting disease as well as concomitant medications and disease will be monitored for 50 % of the patient data. Monitoring will be adapted to the quality of data recorded by the trial site. Monitoring activities will also be adapted to pre-visit checks of the data entered to the eCRF or by telephone visits.

A monitoring visit report will be prepared for each visit describing the progress of the clinical trial and any problems (e.g. refusal to give access to documentation). A follow-up letter will be prepared for the trial site after each visit.

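### Two aspirin contraindications in Protocol 5.3.2 have no matching exclusion criterion, and three more are covered only loosely or in part

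*Protocol*

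**What the plan says.** Protocol 5.3.2 sets out when aspirin 100 mg must not be given. Two of its entries are "severe congestive heart failure" and "combination with methotrexate" at 15 mg per week or more.

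Protocol 4.7 gives the purpose of the eligibility rules: "The selection criteria are chosen to ensure that subjects with specific risks for administration of the study medication" are kept out, together with subjects whose conditions could affect the aims of the study. Protocol 5.8 then states: "All eligible patients will be randomized at baseline visit V1", once the laboratory results needed are available.

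The rules that decide eligibility are the synopsis criteria, 4.11.1 to 4.11.3, and the two groups of excluded therapies in 5.11. The last item of 4.11.3 lets the investigator exclude a patient for reasons that include safety. Under 4.8.1 a patient is withdrawn if the investigator thinks that "continuation of study would bear a potential health risk for the patient". A separate item in 4.8.1 deals with patients who violate or come to violate the in- and exclusion criteria.

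Protocol 7.3.1 sets monitoring at 100 % for "all in- and exclusion criteria, safety parameters and the drug accountability" (as well as the site file and consent). Pre-existing disease is grouped with the lower level: "concomitant medications and disease will be monitored for 50 % of the patient data".

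**The concern.** The protocol treats its two study drugs differently. For rivaroxaban, the contraindications are turned into exclusion criteria. For aspirin, some remain only in the drug description. Half of the planned patients, 94 of 188, are to receive aspirin.

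What is at stake is patient safety. If the named criteria are followed as written, they admit a patient for whom the protocol itself says the control drug is contraindicated. The setting makes heart failure a natural condition to ask about: the trial recruits patients with type 2 diabetes at very high cardiovascular risk, and left ventricular hypertrophy is one of the qualifying findings in 4.11.1. The screening laboratory in 4.15 contains no cardiac marker. NT-proBNP is drawn at V1 and V6 and measured centrally, and no entry rule refers to it.

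**Working it through.** There is no planned figure to reproduce, so the check is a comparison of lists.

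**Step 1. Rivaroxaban.** Each item in 5.2.2 (hypersensitivity, active bleeding, lesions with bleeding risk, other anticoagulants, antiplatelet treatment of ACS after stroke or TIA, hepatic disease with coagulopathy, eGFR below 15 ml/min, conditions with raised bleeding risk, pregnancy and breast-feeding) has a counterpart in 4.11.2, mostly in nearly the same words. Nothing is lost.

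**Step 2. Aspirin.** The items in 5.3.2 against the synopsis, 4.11.2, 4.11.3 and 5.11:

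| Aspirin contraindication (5.3.2) | Counterpart among the entry rules |
|---|---|
| Hypersensitivity | Named in 4.11.2 |
| Ulceration with documented bleeding | Covered; 4.11.2 names current or recent ulceration |
| Tendency to bleed | Covered by the bleeding-risk items of 4.11.2 |
| Last trimester of pregnancy | Covered; 4.11.2 excludes pregnancy at any stage |
| Asthma after salicylates | Not named; covered only if read as hypersensitivity |
| Past GI bleeding caused by NSAIDs | Not named; at best general wording on bleeding risk |
| Liver or kidney failure | Partly: hepatic disease with coagulopathy, eGFR below 15 ml/min |
| Severe congestive heart failure | None |
| Methotrexate at 15 mg per week or more | None |

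For heart failure, the nearest items in 4.11.2 are a major cardiovascular event needing anticoagulation or platelet inhibition, ACS within 12 months, ACS treatment after stroke or TIA, and uncontrolled hypertension. None of these is heart failure. For methotrexate, 4.11.2 excludes other anticoagulants. Section 5.11 excludes strong CYP3A4 and P-gp inhibitors, chronic NSAID use, aspirin above 100 mg per day and other platelet inhibitors. Methotrexate is in none of these groups.

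**Step 3. Other places that might close the gap.** Protocol 5.9 refers to the aspirin SmPC, but only for dosage and frequency. The SAP adds no eligibility rule on this point.

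**Step 4. The path of such a patient.** At screening (4.13.1) the site takes the medical history and records medication from the preceding 12 weeks. At baseline (4.13.2) it checks the criteria and concomitant medication again, and dispensing comes last in that list. Either condition may well come to light at these points. No named criterion then excludes the patient. Exclusion follows only if the investigator acts on 5.3.2 directly or uses the safety item in 4.11.3.

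**Step 5. What naming the conditions would change.** They would come explicitly under the 100 % check of criteria in 7.3.1, instead of the 50 % level for pre-existing disease and concomitant medication. The criteria in 4.11.2 apply before and during the trial, so a patient who developed heart failure or started methotrexate later would fall under the in- and exclusion item of 4.8.1. That item requires immediate withdrawal where safety is concerned and otherwise leaves the decision to the investigator.

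**The case against.** The strongest reply is that the contraindications are already written down. Section 5.3.2 is part of a protocol that investigators must know and sign (3.7.1), and 8.3 demands strict adherence. History and medication are checked at screening, and criteria and medication again at baseline. Section 4.11.3 allows exclusion on safety grounds, and 4.8.1 requires withdrawal if the investigator sees a health risk. On this view only a duplicate entry is missing.

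Much of this stands. The checks lower the risk, and a reader would be wrong to infer that the protocol directs sites to give aspirin to these patients or leaves them to unaided judgement. What the reply does not do is make 5.3.2 an entry rule. The safety provisions in 4.11.3 and 4.8.1 work through the investigator's opinion, whereas the corresponding rivaroxaban risks are fixed criteria.

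It can also be said that 4.11.3 sits under the heading for in- and exclusion criteria, so the 100 % check may already include its safety item. That is a fair reading. Even so, an opinion-based item gives the monitor no named condition to check against.

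Three stronger inferences are tempting and are not supported:

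- **The randomisation request in 5.8.** The site "will send a form containing site ID and screening number to the sponsor", which might suggest that an unnamed condition escapes a check by the sponsor. The form carries no eligibility data for any criterion, named or not, and the proposed change would not alter it.
- **A count of two unnamed items out of nine.** By the test of being named, salicylate asthma and past NSAID-caused bleeding fail as well, and liver or kidney failure passes only in part. Two is the number with no counterpart at all, which is a different statement.
- **A number of unchecked aspirin patients, such as half of 94, or 47.** The protocol speaks of half of the patient data, which need not mean half of the patients, and lets monitoring be adapted to data quality at the site. Monitoring is not stated to precede the first dose, and unchecked records are not affected patients.

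**Conclusion.** The omission is real and can be verified from the text. Severe congestive heart failure and methotrexate at 15 mg per week or more are stated contraindications to the control drug without any corresponding entry rule. Three further aspirin items are unnamed or only partly covered. This departs from the stated purpose in 4.7 and from the protocol's own handling of rivaroxaban.

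The severity is minor. The documents give no prevalence of either condition, so the number of patients affected is unknown and could be zero. Sample size, error rates and analyses are untouched. The conclusion rests on reading the synopsis, 4.11.1 to 4.11.3 and 5.11 as the complete set of entry rules. If a site treats 5.3.2 as binding at entry, the practical risk is smaller still. The point is best labelled a cheap improvement for patient safety.

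**What to change.** Add one line to 4.11.2, and to the synopsis, excluding any patient with a contraindication to either study drug listed in 5.2.2 or 5.3.2, and naming severe congestive heart failure and methotrexate at 15 mg per week or more. Add methotrexate at that dose to the excluded therapies in 5.11. The cross-reference also makes salicylate asthma, past NSAID-caused bleeding and liver or kidney failure explicit, so they need no separate lines.

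The cost is a short amendment and possibly a few fewer eligible patients; the documents do not allow that number to be estimated. The eligibility criteria have been amended before (Amendments 1, 2 and 4), and Amendment 4 notes that such changes need approval from the ethics committee and the competent authority.

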## 5.4 Central pharmacy

The IMP are labelled and shipped to the sites on behalf of the sponsor by the central pharmacy in Dresden. The order of the IMP will be in the responsibility of the sponsor. For queries concerning the IMP use following contact:

Klinik-Apotheke Universitätsklinikum Carl Gustav Carus / TU Dresden [contact] [contact]

## 5.5 Labeling of the IMP

The IMP will be used in its commercially available form. Special labeling for the present study is not necessary according to GCP-V §5 (8) as treatment is unblinded. However, to avoid unauthorized usage the package (primary and secondary packaging) will be marked as containing study medication according to GCP by central pharmacy.

A complete record of batch numbers and expiry dates of all study treatment will be maintained in the ISF. Batch numbers of administered IMP will be recorded in the drug accountability log for each individual patient. All study medication used during the trial will be stored at the study site under controlled conditions (protected from light, at room temperature not exceeding 25°C for aspirin) and will be inaccessible to unauthorized personnel. In case the IMP is expired or stored outside the required temperature limits, the respective batch is not to be used anymore for study purposes and has to be put in quarantine until return.

## 5.6 Drug logistics and accountability

All study drugs will be stored at the study site in accordance with GCP requirements and the instructions given on the package insert and will be inaccessible to unauthorized personnel. Storage conditions and a complete record of batch numbers and expiry dates can be found in the TMF; the site-relevant elements of this information will be available in the ISF. The responsible site personnel will confirm receipt of study drug in writing and will use the study drug only within the framework of this clinical study and in accordance with this protocol. Receipt, distribution, return and destruction (if any) of the study drug must be properly documented according to the sponsor's agreed and specified procedures.

## 5.7 Dispensing of IMP

All packages should be inspected visually before distribution to the study subjects. The IMP will be dispensed to the subjects during the following visits by the site personnel. Each subject will get the following amounts of the randomized IMPs.

Visit Week	V0 day28	V1 day 0 ±4d	V2 2 ±2d	V3( тv) 4 ±2d	V4 8 ±2d	V5( тv) 12 ±2d	V6 20 ±2d	Dispensed medication
Rivaroxa- ban	-	90 Tabl. (3 Packs)	210 Tabl. (7 Packs)	-	330 Tabl. (11 Packs)	-	270 Tabl. (9 Packs)	630 (+270) Tabl. = 21 (+9) Packs
Aspirin	-	50 Tabl. (1 Pack)	50 Tabl. (1 Pack)	-	50 Tabl. (1 Pack)	-	100 Tabl. (2 Packs)	150 (+100) Tabl. = 3 (+2) Packs

 TABLE 9: DRUG DISPENSE FOR FIRST TREATMENT PERIOD (1 PACK RIVAROXABAN CONTAINING 30 TABLETS; 1 PACK ASPIRIN CONTAINING 50 TABLETS);

Visit Week	V7 (TV) 24 ±2d	V8 28 ±2d	V9 (TV) 32 ±2d	V10 36 ±2d	V11 (TV) 40 ±2d	V12 (TV) 44 ±2d	V13 52 ±2d	Dispensed medication
Rivaroxa- ban	-	210 Tabl. (7 Packs)	-	510 Tabl. (17 Packs)	-	-	-	720 Tabl. = 24 Packs
Aspirin	-	50 Tabl. (1 Pack)	-	150 Tabl. (3 Packs)	-	-	-	200 Tabl. = 4 Packs

OPTIONAL: DISPENSE OF IMP AT V6 FOR PATIENTS PARTICIPATIONS TO EXTENDED TREATMENT PERIOD

TABLE 10: DRUG DISPENSE FOR EXTENDED TREATMENT PERIOD (80 OF 188 PATIENTS) (1 PACK RIVAROXABAN CONTAINING30 TABLETS; 1 PACK ASPIRIN CONTAINING 50 TABLETS)

The dispensing of IMP will be recorded in the drug accountability log in the ISF according to provided templates.

Study subject will receive a medication diary for documentation of intake.

# 5.8 Assignment of trial subjects to treatment groups

All eligible patients will be randomized at baseline visit V1 (after necessary laboratory parameters are available) using a central block randomization process based at the sponsor's site. The study site requesting randomization of a patient will send a form containing site ID and screening number to the sponsor (Dept. of Medical Consulting; [contact]**, in the time frame Monday to Friday 8.00 am to 4.00 pm, not on legal holidays). In return, the site will receive a randomization form containing the randomization number and allocation to treatment arm by fax or email within 30 min.

## 5.9 Selection of dosage of IMP and frequency of treatment

Rivaroxaban will be administered at a dose of 5 mg ( $2 \times 2.5$  mg) twice daily (each 12 h), aspirin will be administered at a dose of 100 mg once daily (each 24 h).

The first dose of either study drug will be administered to the participants at the day of randomisation (visit 1). Further administrations take place at Visit 2 (after 2 weeks) and visit 4 (after 8 weeks).

Rivaroxaban will be administered according to the described instructions. Dosage and frequency of aspirin treatment applied in this study will follow the general specifications of the given SmPC. For patients participating in the extended treatment period, drug dispense will additionally take place at visit V6 (after 20 weeks), at visit V8 after 28 weeks and at visit V10 after 36 weeks.

## 5.10 Blinding

Not applicable, open-label study.

## 5.11 Previous and concomitant medication

Rivaroxaban should not be administered concurrently with CYP3A4 and P-gp inhibitors. Coadministration of rivaroxaban with ketoconazole (400 mg once a day) or ritonavir (600 mg twice a day) led to a 2.6 fold / 2.5 fold increase in mean rivaroxaban AUC and a 1.7 fold / 1.6 fold increase in mean rivaroxaban  $CR_{max}R$ , with significant increases in pharmacodynamic effects which may lead to an increased bleeding risk. Therefore, the use of Rivaroxaban is not recommended in patients receiving concomitant systemic treatment with azole-antimycotics such as ketoconazole, itraconazole, voriconazole and posaconazole or HIV protease inhibitors. These active substances are strong inhibitors of both CYP3A4 and P-gp.

Patients who will need the above mentioned therapies are excluded from the study participation.

Care is to be taken if patients are treated concomitantly with medicinal products affecting haemostasis such as non-steroidal anti-inflammatory medicinal products (NSAIDs), acetylsalicylic acid (ASA) and platelet aggregation inhibitors since these drugs generally increase bleeding risk. Patients who need chronic treatment with NSAID or ASA > 100 mg / day or other platelet aggregation inhibitors are excluded from the study participation.

There is no need for monitoring of coagulation parameters during treatment with rivaroxaban in clinical routine. However, if clinically indicated rivaroxaban levels can be measured by calibrated quantitative anti-Factor-Xa tests.

5.11.1 Dosing recommendations before and after invasive procedures, surgical intervention and rescue therapy for clinical emergencies:

If an invasive procedure or surgical intervention is required, Rivaroxaban should be stopped at least 12 hours before the intervention, if possible and based on the clinical judgement of the physician. If a patient is to undergo elective surgery and anti-platelet effect is not desired, platelet aggregation inhibitors should be discontinued as directed by the manufacturer's prescribing information.

If the procedure cannot be delayed the increased risk of bleeding should be assessed against the urgency of the intervention.

The estimated half life of rivaroxaban is 7 to 11 hours; for aspirin irreversible inhibits platelet aggregation.

Both substances have a wide therapeutic window. Therefore, in case of asymptomatic overdosing without overt bleeding complications no specific treatment actions need to be taken and patient should be kept under surveillance. For rivaroxaban, gastrointestinal uptake can be reduced by activated carbon application within 3 h after intake of rivaroxaban, the same is applicable for aspirin. Aspirin might be removed from the circulation by hemodialysis. No specific antidot is available for either drug. In case of bleeding complications study treatment should be interrupted and symptomatic therapy (fluid resuscitation and blood transfusion as well as mechanical measures to control bleeding) should be initiated immediately. In the case of aspirin further bleeding can be prevented by platelet transfusion. In the case of rivaroxaban therapy with prothrombin complex or recombinant factor VIIa should be considered.

